2.1.3 Recruitment Strategies

Both men and women and members of all races and ethnic groups are eligible for this trial. This study will be listed on NIH websites and www.clinicaltrials.gov. Participants will be recruited from the current patient population as well as referrals at NIH. Social media platforms managed by NIH/NCI may also be used to publicize the study. This protocol may be abstracted into a plain language announcement posted on NIH websites and on NIH social media platforms.

2.2 SCREENING EVALUATION

2.2.1 Screening activities performed prior to obtaining informed consent

Minimal risk activities that may be performed before the subject has signed a consent include the following:

- Email, written, in person or telephone communications with prospective subjects
- Review of existing medical records to include H&P, laboratory studies, etc.
- Review of existing MRI, x-ray, or CT images
- Review of existing photographs or videos
- Review of existing pathology specimens/reports from a specimen obtained for diagnostic purposes

2.2.2 Screening activities performed after a consent for screening has been signed

The following activities will be performed only after the subject has signed the consent for study # 01C0129 (Eligibility Screening and Tissue Procurement for the NIH Intramural Research Program Clinical Protocols). Assessments performed at outside facilities or on another NIH protocol within the timeframes below may also be used to determine eligibility once a patient has signed the consent.

- All tumors will undergo central pathology review at NIH prior to study including molecular CNS panel whenever possible. Archival samples from surgery will be used for pathology review.
- Clinical Evaluations (within 7 days prior to enrollment):
 - Complete history and physical exam completed by principal or associate investigator, including thorough documentation of signs and symptoms caused by the tumor, determination of Karnofsky performance scale (KPS), neurological function and mental status.
 - Vital signs: including height and weight
- Laboratory Evaluations: Pre-treatment blood tests should be performed within 14 days prior to enrollment
 - Hematology: complete blood count (CBC) with differential, PT/INR, PTT

- Chemistries: bilirubin (total and direct), AST, ALT, LDH, BUN, alkaline phosphatase, albumin, serum creatinine, serum electrolytes, calcium, magnesium, phosphorus, uric acid, amylase and lipase
- Hepatitis A, B and C serologies
- HIV antibody test screening.
- Urinalysis
- Serum/urine pregnancy test: required for females of childbearing potential
- Conventional MRI (if needed based upon PI discretion)

2.3 PARTICIPANT REGISTRATION AND STATUS UPDATE PROCEDURES

Registration and status updates (e.g. when a participant is taken off protocol therapy and when a participant is taken off-study) will take place per CCR SOP ADCR-2, CCR Participant Registration & Status Updates found at: [https://nih.sharepoint.com/sites/NCI-CCR-OCD-Communications/SitePages/OEC-Administrative---Clinical-Research-\(ADCR\).aspx?Mode=Edit](https://nih.sharepoint.com/sites/NCI-CCR-OCD-Communications/SitePages/OEC-Administrative---Clinical-Research-(ADCR).aspx?Mode=Edit).

2.3.1 Treatment Assignment Procedures

Cohorts

| Number | Name | Description |
|---------------|-------------|---|
| 1 | Cohort 1 | Patients with newly diagnosed glioblastoma or gliosarcoma |

Arms

| Number | Name | Description |
|---------------|----------------------|---|
| 1 | Experimental therapy | Selinexor with temozolomide and radiation |

Arm assignment

Patients in cohort 1 will be directly assigned to arm 1. No randomization and stratification will be performed on this study.

2.4 BASELINE EVALUATION

Baseline assessments will be performed per **Study Calendar**. Tests done at screening do not need to be repeated on baseline (C1D1) if performed within 7 days prior to enrollment except for physical exam, KPS, vital signs, neurological exam, performance and mental status, and urine pregnancy test. Screening laboratory evaluations do not need to be repeated if performed within 14 days prior to enrollment. Please refer to section **2.2** for screening details.

- Thyroid function tests: total T3, freeT4 and TSH+
- Treatment planning CT/MRI scans: All patients will have radiation therapy treatment planning CT and MRI scans (as explained below). Treatment planning CT scans will be obtained with immobilization mask in place.

- Conventional MRI: Conventional MRI including T1, T2, T2 FLAIR and postcontrast T1 as well as diffusion weighted (DWI) MRI (NOB Procedure DCE MRI) of the brain to occur within 2 weeks prior to study entry. If scans were obtained from another institution copies should be produced and maintained on file with the PI for future comparison, the patient however must receive MRI imaging as per above. MRI of the brain obtained within 2 weeks prior to enrollment can be used as baseline staging evaluations to be done at the NIH.
- If initial imaging evaluation was greater than 3 weeks prior to referral, a diagnostic quality contrast enhanced MRI will be obtained for baseline staging evaluation.
- Baseline quality of life (QOL) will be collected as per the MD Anderson Symptom Inventory for Brain Tumors (MDASI-BT) ([Appendix D](#)), PROMIS Depression, PROMIS Anxiety, and NeuroQoL assessments ([Appendix E](#)), PRO-CTCAE ([Appendix F](#)) within 1 week of study entry.

3 STUDY IMPLEMENTATION

3.1 STUDY DESIGN

[figure not shown]
3.1.1 Concurrent Therapy

- Radiation therapy (RT) will be administered daily (Monday to Friday) in the Radiation Oncology Branch (ROB), NCI, unless the treatment schedule requires change in the event of inclement weather or federal holidays.
- Oral temozolomide will be taken as described in section [3.2.1](#).
- Selinexor will be given during radiation as determined by dose level. Please refer to section [3.1.5](#) for details. All the protocol related follow-up appointments will occur at NCI ROB.

3.1.2 Adjuvant Therapy

- Post RT, temozolomide will be given per standard of care. It could be given under this study or by patient's primary oncologist.

3.1.3 Study Schema

3.1.4 Dose Limiting Toxicity

A dose-limiting toxicity (DLT) is defined as a clinically significant adverse event assessed as unrelated to tumor progression, intercurrent illness or concomitant medications and meets any of the criteria below. Any DLT must be a toxicity considered at least possibly related to selinexor and the acute effects thereof.

- Any grade 3 or 4 toxicity as per CTCAE Criteria Version 5.0 during treatment and within 30 days after completion of RT
- Any grade 3 or 4 toxicity as per Section **14.1.2.** RTOG acute morbidity during treatment and within 30 days after completion of RT
- Any toxicity at least possibly related to selinexor that causes a patient to miss consecutive radiation or temozolomide doses for 5 days.

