3.2 DRUG ADMINISTRATION

3.2.1 Selinexor

At dose level 1, Selinexor will be administered orally at an initial dose of 80 mg. The first dose will be given on day 2 of radiation and will thereafter be administered weekly on the second day of weekly radiation on weeks 1, 2, 4, and 5. If dose level 1 is tolerated, the Selinexor dose will be escalated to 60 mg twice a week on weeks 1, 2, 4, 5 given on Monday and Thursday. The third and final dose level will be 60 mg administered twice a week (on Monday and Thursday of radiation) for 6 weeks.

Prophylactic concomitant treatments with a 5-HT3 antagonist and olanzapine may be administered per section [4](#).

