4 CONCOMITANT MEDICATIONS/MEASURES

- Prophylactic concomitant treatments with a 5-HT3 antagonist and olanzapine 5 mg for men and 2.5 mg for women must be provided 3 days prior to and during treatment with each dose of selinexor. Olanzapine may be administered as needed on days 6 and 7 during week of selinexor treatment.
- PJP prophylaxis should be given during the concurrent chemoradiation phase of treatment. Acceptable forms of treatment include oral trimethoprim-sulfamethoxazole and aerosol pentamidine as is left to the discretion of the treating physician.
- Other cancer chemotherapy, immunotherapy, or investigational agents may NOT be administered to patients in the active course of treatment on this study.
- Patients will receive corticosteroids as needed for symptoms of cerebral edema as clinically indicated. Attempts to wean patients from steroids should be made as indicated by improvement or stabilization of neurologic symptoms. Any initiation of steroids or increase in dose thereof will be documented.
- All patients with a seizure history will be maintained on their existing anticonvulsant medication.

- Radiation therapy side effects include fatigue, nausea and vomiting and possible worsening of preexisting neurological symptoms. These will be managed using general best supportive care and corticosteroids may be initiated at the discretion of the treating radiation oncologists and taper as needed depending on clinical status once irradiation has been completed.
- The ROB staff physician, nurse practitioner and research nurse will frame the support infrastructure required to assist with the patient's care in the event of serious treatment toxicity. The pain and palliative team, will be consulted as needed to address end of life issues and disposition as has been standard procedure for all ROB patients to date.

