8.1.6 Relationship to Study Product

All AEs will have their relationship to study product assessed using the terms: related or not related.

- Related – There is a reasonable possibility that the study product caused the adverse event. Reasonable possibility means that there is evidence to suggest a causal relationship between the study product and the adverse event.
- Not Related – There is not a reasonable possibility that the administration of the study product caused the event.

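### Read literally, section 3.1.4 drops a grade 3-4 event from the DLT count if a co-medication may have contributed, even when selinexor may have too; the MTD can then be pushed upward by an unknown amount.

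*Combined protocol and SAP*

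**What the plan says.** Section 3.1.4 sets two conditions that apply to every DLT. The event must be "assessed as unrelated to tumor progression, intercurrent illness or concomitant medications and meets any of the criteria below". The next sentence adds: "Any DLT must be a toxicity considered at least possibly related to selinexor". The main severity criterion is "Any grade 3 or 4 toxicity as per CTCAE Criteria Version 5.0 during treatment and within 30 days after completion of RT".

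Section 4 plans the co-medication. A 5-HT3 antagonist and olanzapine "must be provided 3 days prior to and during treatment with each dose of selinexor". Section 3.2.1 words the same treatment differently: "Prophylactic concomitant treatments with a 5-HT3 antagonist and olanzapine may be administered per section" 4. Section 4 also states that "PJP prophylaxis should be given during the concurrent chemoradiation phase of treatment". Corticosteroids are given as needed, and existing anticonvulsants continue in patients with a seizure history.

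Section 8.1.6 has the only causality scale. It has two categories, related and not related, and it grades relationship to the study product only. Its lower category reads: "There is not a reasonable possibility that the administration of the study product caused the event". Section 8.2 collects an alternate etiology only where the event is judged not related to study product.

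Two other sections attribute toxicity in their own ways. The MTD definition in 3.1.5 refers to DLTs resulting from selinexor, RT and temozolomide together. The accrual halt in 3.1.6 needs only possible attribution to selinexor and has no co-medication exclusion.

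**The concern.** The two conditions in 3.1.4 are joint: the second does not override the first. Suppose an assessor thinks selinexor possibly caused a grade 3 event but cannot call it unrelated to olanzapine. The event meets the selinexor condition and fails the exclusion condition. No section says how to classify it. The protocol does foresee mixed causes, since the notes to the selinexor dose-adjustment table in 3.3.2.1 mention events thought to be multifactorial.

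The clause works in one direction: it can remove events from the DLT count but never add any. In cohorts of three, one reclassified patient changes the decision. One DLT in three becomes none, and the level is passed without expansion. Two in three becomes one, and the level is expanded instead of escalation stopping. The count drives the MTD, which is the primary endpoint (10.1.1) and, by 3.1.5, generally the recommended phase 2 dose. Two assessors could also classify the same event differently and both follow the text.

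**Working it through.** **Attribution standards side by side**

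| Section | Use | Standard |
|---|---|---|
| 3.1.4, first sentence | DLT | unrelated to progression, intercurrent illness, concomitant medications |
| 3.1.4, second sentence | DLT | at least possibly related to selinexor |
| 3.1.5 | MTD | DLT resulting from selinexor, RT and temozolomide |
| 3.1.6 | accrual halt | possibly attributable to selinexor |
| 8.1.6 | all AEs | related or not related to study product |

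A treatment interruption of five consecutive days appears both as the third DLT criterion in 3.1.4 and as the halt trigger in 3.1.6. Under the literal wording, a mixed-cause interruption counts toward the halt but not toward the MTD. The halt does not pick up grade 3-4 events that cause no such interruption.

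**The plan's own figures**

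Under the 3.1.5 table, escalation follows 0/3 DLTs, or 1/3 and then 0/3. With DLT probability p:

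E(p) = (1−p)³ + 3p(1−p)² × (1−p)³ = (1−p)³ + 3p(1−p)⁵

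At p = 10, 20, 30, 40, 50 and 60% this gives 0.906, 0.709, 0.494, 0.309, 0.172 and 0.082. The table in 10.2 (.91, .71, .49, .31, .17, .08) is reproduced.

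**Effect of uncounted DLTs**

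Let f be the share of true DLTs not counted because of the clause, so that the counted rate is p(1−f). The documents give no value for f; every value here is an assumption. At a true rate of 30%:

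| f | counted rate | E |
|---|---|---|
| 0 | 0.300 | 0.343 + 0.151 = 0.49 |
| 10% | 0.270 | 0.389 + 0.168 = 0.56 |
| 25% | 0.225 | 0.465 + 0.189 = 0.65 |
| one third | 0.200 | 0.512 + 0.197 = 0.71 |
| 50% | 0.150 | 0.614 + 0.200 = 0.81 |

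At a true rate of 40%, E is 0.31, 0.38, 0.49 and 0.71 for f = 0, 10%, 25% and 50%.

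**Effect on the selected dose**

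Level 3 is chosen if levels 1 and 2 are passed and at most 1 of 6 patients at level 3 has a counted DLT:

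P(level 3) = E(p₁) × E(p₂) × [(1−p₃)⁶ + 6p₃(1−p₃)⁵]

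With assumed true rates of 10/25/40% and f = 0, this is 0.906 × 0.600 × 0.233 = 0.13.

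| Assumed true rates, levels 1/2/3 | f = 0 | 10% | 25% | 50% |
|---|---|---|---|---|
| 10/25/40% | 0.13 | 0.18 | 0.29 | 0.55 |
| 20/30/45% | 0.06 | 0.09 | 0.18 | 0.44 |

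**The case against.** The first sentence of 3.1.4 can be read as removing only events that another cause explains, with the second sentence then setting a deliberately low threshold for selinexor. Section 8.2 fits that reading, because it looks for another cause only once the study product has been judged not related. This stands as a possible reading. The protocol does not adopt it, and the word used is the stricter one.

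A reader might import the 8.1.6 definition and infer that any reasonable possibility of a co-medication effect removes an event. The documents do not support that step: 8.1.6 grades relationship to the study product and gives no scale for other drugs.

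A reader might also infer that overlap is frequent, because section 14.1.2 lists effects such as fatigue, confusion, high blood sugar and low neutrophils for selinexor. Section 4 gives no adverse-effect profile for the co-medications, so the frequency of overlap cannot be taken from the documents.

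Nor is everything in section 4 required with selinexor. Only the 5-HT3 antagonist and olanzapine are tied to its dosing, and sections 4 and 3.2.1 disagree on whether they are mandatory. PJP prophylaxis belongs to chemoradiation, and steroids and anticonvulsants apply to some patients.

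Finally, 3.1.4 has no carve-out for expected or transient grade 3-4 events, which pushes the count the other way, and the halt in 3.1.6 is untouched by the exclusion. Both points stand. They limit what can be said about net bias in the MTD but do not repair the clause.

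**Conclusion.** The point holds as a defect of wording with a known direction and an unknown size. Followed literally, 3.1.4 excludes a grade 3-4 event that is possibly due to both selinexor and a co-medication. No other section corrects this.

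It would go too far to conclude that such events are certainly excluded, or that the MTD is biased high. The first depends on which reading assessors adopt. The second depends on how often they exclude mixed-cause events, and on the rest of the DLT definition. At f = 0 there is no effect. Over the assumed range of 0 to 50% lost, the probability of escalating at a true rate of 30% runs from 0.49 to 0.81.

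A reader might also infer that temozolomide is a concomitant medication under this clause. The protocol does not say so. The title page lists temozolomide as a study drug under the IND, and 3.1.5 includes it in the regimen to which DLTs are attributed, which points the other way.

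The clause should be changed because it bears on the primary endpoint and the correction is small.

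**What to change.** - In 3.1.4, make the exclusion apply to events *not clearly attributable solely to* tumor progression, intercurrent illness or a concomitant medication, in place of the requirement that they be unrelated to these. Keep the sentence requiring at least possible relation to selinexor.
- Align the attribution wording in 3.1.5 and 3.1.6 with the revised 3.1.4.
- Record the alternative cause for any grade 3-4 event judged possibly related to selinexor but not counted as a DLT. Section 8.2 already covers events judged not related to study product, so this adds only the missing group.
- Reconcile sections 4 and 3.2.1 on whether the antiemetic and olanzapine are mandatory. Which is right is for the sponsor to decide.

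The cost is one reworded clause, matching edits in two sections and one extra recorded item. The downside is that some mixed-cause events will count as DLTs, so escalation becomes slightly more conservative. How patients are treated for toxicity does not change.

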3.1.5 Dose Escalation

This study will use a 3+3 design, with 3-6 patients enrolled per dose level to define maximum tolerated dose (MTD). The MTD is the dose level at which no more than 1 of up to 6 patients experience DLT within 1 month of completion of treatment, and the dose below that at which at least 2 (of ≤6) patients have DLT as a result of selinexor/RT/temozolomide. If a patient did not experience DLT and did not finish treatment, he or she will not be evaluable for toxicity and will be replaced in the dose level. Enrollment to a dose level would stop if 2 or more patients had a DLT.

The number of patients may be increased to 9 total patients at the MTD (provided no DLT) with a maximum of 21 evaluable patients enrolled and the minimum evaluable patients required will be 15. The once weekly dosing schedule was based on the results of the KCP-330-004 study Arm D. The twice weekly dose of 60mg is from KCP-330-004 Arm C.

| Dose Escalation Schedule of Selinexor | |
|--|--|
| Dose Level | |
| Level -1 | 80 mg on weeks 1, 4 |
| Level 1 | 80 mg on weeks 1, 2, 4, 5 |
| Level 2 | 60 mg twice a week on weeks 1, 2, 4, 5 |
| Level 3 | 60 mg twice a week, weeks 1-6 |

All patients will receive 2Gy daily RT plus 75mg/m² temozolomide.

Dose escalation will follow the rules outlined in the Table below.

| Number of Patients with DLT at a Given Dose Level | Escalation Decision Rule |
|---|--|
| 0 out of 3 | Enter up to 3 patients at the next dose level |
| ≥ 2 | Dose escalation will be stopped. This dose level will be declared the maximally administered dose (highest dose administered). Up to three (3) additional patients will be entered at the next lowest dose level if only 3 patients were treated previously at that dose. |
| 1 out of 3 | Enter up to 3 more patients at this dose level. 
• If 0 of these 3 patients experience DLT, proceed to the next dose level.• If 1 or more of this group suffer DLT, then dose escalation is stopped, and this dose is declared the maximally administered dose. Up to three (3) additional patients will be entered at the next lowest dose level if only 3 patients were treated previously at that dose. |
| ≤ 1 out of 6 at highest dose level below the maximally administered dose | This is the MTD and is generally the recommended phase 2 dose. At least 6 patients must be entered at the recommended phase 2 dose. |

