3.2.2 Temozolomide

Temozolomide will begin on the first day or evening prior of radiation and be administered orally daily at a dose of 75 mg/m^2 during the radiation treatment. Temozolomide will continue until the completion of radiation and then will be stopped.

Beginning 1-month post-RT, the adjuvant temozolomide will be given per standard of care.

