3.3.2.2.2 Following the completion of chemoradiation

Beginning 1-month post-RT, the adjuvant temozolomide will be given per standard of care.

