10.2 SAMPLE SIZE DETERMINATION

The primary objective of this trial is to determine the safety, toxicity profile, DLT and maximum tolerated dose (MTD) of Selinexor given concurrently alongside temozolomide and radiation in patients with newly diagnosed glioblastoma patients. There are 3 planned dose levels for this trial that will enroll 1 to 6 patients each using the 3+3 design to define the MTD. The MTD will be based on the assessment of DLT within one month following the irradiation, and will be defined as the dose level at which less than one-third of patients (0/3 or 0-1/6 patients) treated at that dose level experience a DLT, with the next higher dose level demonstrating a one-third or greater number of patients ($\geq 2/3$ or $\geq 2/6$ patients) having DLT. If a patient did not experience DLT and did not finish therapy, he or she will not be evaluable for determination of the MTD

and will be replaced in the dose level. An additional 3 to 6 patients will be enrolled at the MTD, so that a total of 9 patients will be treated at this dose to better characterize the clinical activity of this combination in this patient population. Thus, if all 3 dose levels are evaluated (6 patients per dose level with 9 total patients at the MTD or maximum administered dose), a maximum of 21 evaluable patients will be enrolled. Similarly, if all dose levels are evaluated, the minimum number of evaluable patients required will be 15. To compensate for inevaluable patients, an additional 3 patients may be enrolled. Thus, a maximal of 24 patients are targeted for this study. It is expected that accrual can be completed in 24 months.

Using this dose escalation scheme, the probability of escalating to the next dose level, based on the true rate of DLT at the current dose, is given by the following table (each group will be considered independently of the other):

| True rate of DLT at a given dose | 10% | 20% | 30% | 40% | 50% | 60% |
|----------------------------------|-----|-----|-----|-----|-----|-----|
| Probability of escalating | .91 | .71 | .49 | .31 | .17 | .08 |

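### Both graded DLT criteria stop at grade 4, so a selinexor-related death late in radiotherapy or in the following 30 days, with no earlier related grade 3-4 event, meets no listed DLT criterion

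*Combined protocol and SAP*

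**What the plan says.** Section 3.1.4 makes an event a DLT only if it meets at least one of three criteria. It must also be at least possibly related to selinexor and its acute effects, and unrelated to progression, intercurrent illness or concomitant medication.

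- **CTCAE:** "Any grade 3 or 4 toxicity as per CTCAE Criteria Version 5.0 during treatment and within 30 days after completion of RT".
- **RTOG acute morbidity:** the same grades, 3 or 4, and the same window.
- **Missed doses, with no grade limit:** "Any toxicity at least possibly related to selinexor that causes a patient to miss consecutive radiation or temozolomide doses for 5 days".

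There is no catch-all. Section 10.1.1 confirms that toxicity is assessed for escalation up to 30 days after radiotherapy.

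Concurrent temozolomide ends with radiotherapy (3.2.2: "Temozolomide will continue until the completion of radiation and then will be stopped"). Section 3.3.2.2.2 then says: "Beginning 1-month post-RT, the adjuvant temozolomide will be given per standard of care".

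Under 3.1.5, a patient who "did not experience DLT and did not finish treatment, he or she will not be evaluable for toxicity and will be replaced". Section 10.2 agrees: "If a patient did not experience DLT and did not finish therapy, he or she will not be evaluable for determination of the MTD". Section 3.1.5 also stops enrolment to a level at 2 or more DLTs and makes the increase to 9 patients at the MTD conditional on there being no DLT.

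**The concern.** The primary endpoint is the MTD, which rests on counts of 0, 1 or 2 DLTs among 3 to 6 patients. How one patient is scored can change a decision.

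The two graded criteria use a closed range that leaves out the fatal grade. The third can reach a death only while 5 days of radiation or temozolomide remain to be missed. Late in radiotherapy, and for the 30 days after it, a related death without a preceding related grade 3-4 event has no criterion to meet. The most serious toxicity could then be recorded as no DLT in a period that the plan set aside for counting DLTs.

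Level 3 is the most exposed by schedule: "The third and final dose level will be 60 mg administered twice a week (on Monday and Thursday of radiation) for 6 weeks". Its last doses fall in the final week of radiotherapy.

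**Working it through.** **1. The plan's own table.** With true DLT rate p, the 3+3 rule escalates with probability f(p) = (1−p)³ + 3p(1−p)⁵. At p = 10%, 20%, 30%, 40%, 50% and 60% this gives 0.906, 0.709, 0.494, 0.309, 0.172 and 0.082. All six match the table in 10.2. The gap does not affect the table, which takes the DLT rate as given.

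**2. When the gap is open.** Inputs: 30 fractions, 5 per week (3.6.2), and the selinexor schedules in 3.1.5 and 3.2.1. Assumptions: a Monday start and no interruption. Radiotherapy ends on day 40 and the DLT window on day 40 + 30 = day 70.

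| Level | Last selinexor dose(s) | Fractions left after it |
|---|---|---|
| 1 | day 30 | 8 |
| 2 | day 32 | 6 |
| 3 | days 36 and 39 | 4 and 1 |

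Fewer than 5 fractions remain once the day 36 fraction is given. The gap is therefore days 37 to 70, which is 34 days. That starts after 6 days from the last level 1 dose and 4 days from the last level 2 dose. Treatment is unfinished on days 37 to 40 only. For the other 30 days it is finished, so the literal result is mostly a DLT-free score and seldom replacement.

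**3. Effect on one cohort (death scored DLT-free).**

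| Level | True count | Read as | Consequence |
|---|---|---|---|
| 1 or 2 | 1/3 | 0/3 | escalate instead of entering 3 more |
| 1 or 2 | 2/3 | 1/3 | enter 3 more instead of stopping |
| 3 | 2/6 | 1/6 | MTD declaration changes |

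At level 3 the stop on enrolment and the condition for expanding to 9 are affected as well.

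**4. Illustration of size.** The documents give no rate for such deaths. Assume a total DLT-level rate p = 0.40, of which q = 1%, 2% or 4% of patients have an uncounted death. The counted rate is r = p − q, and the chance of escalating is f(r).

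- q = 1%: f(0.39) = 0.326
- q = 2%: f(0.38) = 0.62³ + 3(0.38)(0.62⁵) = 0.238 + 0.104 = 0.343
- q = 4%: f(0.36) = 0.378

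The reference is f(0.40) = 0.309, so the rises are 0.0165, 0.0335 and 0.0688.

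**5. Where the rise comes from (q = 2%).**

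- First 3 patients read 0/3 when at least one event occurred, net of cases that would have escalated anyway: (0.62³ − 0.60³) − 3(0.02)(0.60²)(0.60³) = 0.0223 − 0.0047 = 0.0177.
- First 3 correctly read 1/3, next 3 wrongly read 0/3: 3(0.38)(0.60²)(0.62³ − 0.60³) = 0.0092.
- First 3 read 1/3 when 2 or more events occurred, next 3 read 0/3: 3(0.38)(0.62² − 0.60²)(0.62³) = 0.0066.

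The sum is 0.0335. A group of three wrongly read as 0/3 accounts for about four fifths, more than half of the total arising in the first three patients. The 1/3-for-2/3 misreading accounts for about one fifth.

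**6. Sensitivity to p.** With q = 2%, the rise is 0.043, 0.042, 0.033 and 0.023 at p = 20%, 30%, 40% and 50%.

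**The case against.** The strongest reply is that the gap is nearly empty and that intent is clear. Every DLT must be tied to the acute effects of selinexor. Section 1.2.7.1.1 gives a half-life of about 5 to 8 hours, and at levels 1 and 2 the gap opens 4 to 6 days after the last dose. A slower toxicity such as cytopenia would usually reach grade 3 or 4 first and already be a DLT. The background on the recurrent-glioma study (1.2.7.3.2) speaks of grade 5 DLTs, so the authors evidently regard death as a DLT grade. Weekly team review (7.4.1), death and SAE reporting (7.3, 8.3, 8.4) and the suspension clause (13.1) would bring any such death to attention.

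This stands as an argument that the event is rare and that the team would probably count it. It does not close the gap: none of these sections makes the death a DLT, and the background sentence concerns another study.

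A second reply is that the missed-dose criterion states no window, so missed adjuvant temozolomide might bring the death in. Adjuvant dosing starts 1 month after radiotherapy, about when the DLT window closes, and under 3.1.2 it may be given outside the study. That reading does not make the death expressly a DLT.

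A reader might infer that this plan never counts a treatment-related death. The documents do not support that. A related death with 5 or more treatment days still due meets the missed-dose criterion on a natural reading, and one preceded by a related grade 3-4 event is already a DLT.

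**Conclusion.** The point holds in this narrow form and should be fixed. Followed literally, the DLT definition leaves out a related death in the last few radiotherapy days or the next 30 days when no related grade 3-4 event came first. The patient is then scored DLT-free, or is replaced if treatment was unfinished.

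On the assumed 1% to 4% uncounted at a 40% total DLT rate, the chance of escalating rises by about 0.02 to 0.07. Those rates have no source in the documents and serve only to show scale. The calendar assumes a Monday start and uninterrupted treatment.

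Two stronger inferences are not supported. The plan does not show an intention to tolerate such deaths, and its safety reporting would not miss them; what is absent is a rule for scoring them. Nor is the escalation table in 10.2 wrong, since it reproduces at all six rates.

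**What to change.** The sponsor should reconcile 3.1.4 with the replacement rule in 3.1.5 and 10.2. The CTCAE criterion should state expressly how a grade 5 event at least possibly related to selinexor, within the DLT window, is classified. The replacement wording should follow from that, so that no such patient is scored DLT-free or replaced by default. The RTOG criterion need not change, because the acute scale printed in Appendix B ends at grade 4.

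The cost is a few words in a protocol amendment, with no extra patients or procedures.
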